1.3.2 Primary Endpoint

The primary endpoint is a composite rate of all death or all myocardial infarction (Academic Research Consortium [ARC]) from 3 months to 12 months.

1.3.3 Secondary Endpoint(s)

1.3.3.1 Major Secondary Endpoint(s)

- Major bleeding rate (BARC type 2-5) from 3 to 12 months.
- Stent thrombosis (ARC definite/probable) from 3 to 12 months

1.3.3.2 Other Secondary Endpoint(s)

The following endpoints will be assessed from 3 to 12 months:

- All death, cardiac death, vascular death, non-cardiovascular death
- All MI (modified ARC) and MI attributed to target vessel (TV-MI, modified ARC)
- Composite of cardiac death or MI (modified ARC)
- All stroke, ischemic stroke and hemorrhagic stroke
- Clinically-indicated target lesion revascularization (CI-TLR)
- Clinically-indicated target vessel revascularization (CI-TVR)
- Target lesion failure (TLF, composite of cardiac death, TV-MI and CI-TLR)
- Target vessel failure (TVF, composite of cardiac death, TV-MI and CI-TVR)
- Major bleeding defined by the Bleeding Academic Research Consortium (BARC) type 3-5

1.4 Analysis Populations

Primary Analysis Population

The primary analysis population includes “3-month clear” population, defined as subjects who are free from myocardial infarction (modified ARC), repeat coronary revascularization, stroke, or stent thrombosis (ARC definite/probable) within 3 months [REDACTED]

[REDACTED] after stenting AND have been compliant with 3-month dual antiplatelet therapy

(DAPT) [REDACTED]

1.5 Sample Size Calculations

- Sample size in the control arm (3-month clear): ~1,150

A total sample size of 2,000 subjects in the XIENCE 90 study will be required for this test.

[REDACTED]

[REDACTED]

[REDACTED]

2. ANALYSIS CONSIDERATIONS

2.1 Statistical Methods

Baseline demographic, clinical, angiographic, procedural, and device data, and clinical results will be summarized using descriptive summary statistics.

2.1.1 Descriptive Statistics for Continuous Variables

For continuous variables (e.g., age, percent diameter stenosis and lesion length), results will be summarized with the numbers of observations, means, and standard deviations and where specified in the table mockups, with quartiles, minimums, maximums, and two-sided 95% confidence intervals for the means as per the table mockups. Differences between two comparison groups of interest, where specified, will be summarized with the differences of the two means, and two-sided 95% confidence intervals for the difference between the means. These calculations will be done under the assumption that the data for the two arms are independent and approximately normal in distribution. The confidence interval for the difference of two means will be calculated under the assumption of unequal variances. If the asymptotic assumptions fail, then nonparametric summary statistics (medians, 25th and 75th percentiles) may be displayed as an alternative.

Formulas for calculation of the confidence intervals for the continuous variables are given below:

1. 100(1- α)% Confidence Interval For A Single Mean⁵

$$\bar{x} \pm t_{\frac{\alpha}{2}} \frac{s}{\sqrt{n}}$$

where:

\bar{x} = sample mean

s = sample standard deviation

n = sample size

$t_{\frac{\alpha}{2}}$ = the alpha/2 t - statistic for $n - 1$ degrees of freedom

2. 100(1- α)% Confidence Interval For The Difference of Two Means Under The Assumption Of Equal Variances Between The Two Groups⁵

$$(\bar{x}_1 - \bar{x}_2) \pm t_{\frac{\alpha}{2}} \sqrt{s_p^2 \left(\frac{1}{n_1} + \frac{1}{n_2} \right)}$$

where:

\bar{x}_1 = sample mean for group 1

\bar{x}_2 = sample mean for group 2

$$s_p^2 = \frac{(n_1 - 1)s_1^2 + (n_2 - 1)s_2^2}{n_1 + n_2 - 2}$$

s_1 = sample standard deviation for group 1

s_2 = sample standard deviation for group 2

n_1 = sample size for group 1

n_2 = sample size for group 2

$t_{\frac{\alpha}{2}}$ = the alpha/2 t - statistic for $n_1 + n_2 - 2$ degrees of freedom

3. 100(1- α) % Confidence Interval for the Difference of Two Means under the Assumption of Unequal Variances between the Two Groups⁵

$$(\bar{x}_1 - \bar{x}_2) \pm t_{\frac{\alpha}{2}} SED$$

With the degrees of freedom for the approximate t statistic is determined by Satterthwaite's formula² as follows:

$$df = \frac{(w_1 + w_2)^2}{\frac{w_1^2}{n_1 - 1} + \frac{w_2^2}{n_2 - 1}}$$

where:

\bar{x}_1 = sample mean for group 1

\bar{x}_2 = sample mean for group 2

s_1 = sample standard deviation for group 1

s_2 = sample standard deviation for group 2

n_1 = sample size for group 1

n_2 = sample size for group 2

$$SED = \sqrt{\frac{s_1^2}{n_1} + \frac{s_2^2}{n_2}}$$

$$w_1 = \frac{s_1^2}{n_1}$$

$$w_2 = \frac{s_2^2}{n_2}$$

2.1.2 Descriptive Statistics for Categorical Variables

For categorical variables such as gender, Death/MI and TLF, results will be summarized with subject counts and percentages/rates, [REDACTED] with exact two-sided 95% Clopper-Pearson⁶ confidence intervals. Differences between two comparison groups of interest, when specified, will be summarized with the difference in percentages and the Newcombe⁵ score two-sided 95% confidence interval for the difference of two percentages.

For efficacy and safety endpoint(s), relative risks (i.e., the ratio of rates), confidence interval for the relative risks, the difference in rates and the confidence interval for difference in rates (using previously-described formulas), and p-values may also be presented for hypothesis generating purposes. The p-values will be based on either Pearson's Chi-square test or Fisher's exact test by checking the expected frequency for each cell in the 2x2 contingency table against Cochran's rule⁸, i.e., if the expected frequencies for all cells are ≥ 5 , then Pearson's Chi-square test will be used, otherwise Fisher's exact test will be used.

[REDACTED]

[REDACTED]

[REDACTED]

[REDACTED]

[REDACTED]

Formulas for calculating confidence intervals for the categorical variables are given below.

1. 100(1- α) % Exact Clopper-Pearson Confidence Interval for A Single Proportion⁶

$$\text{Lower Confidence Limit} = \frac{x}{x + (n - x + 1)F_{1-\frac{\alpha}{2}}(2(n - x + 1), 2x)}$$

$$\text{Upper Confidence Limit} = \frac{(x + 1)F_{1-\frac{\alpha}{2}}(2(x + 1), 2(n - x))}{n - x + (x + 1)F_{1-\frac{\alpha}{2}}(2(x + 1), 2(n - x))}$$

where:

n = sample size

x = number of "events"

$F_{1-\frac{\alpha}{2}}(df_1, df_2)$ = the $(1 - \alpha/2)$ F - statistic for degrees of freedom df_1 and df_2

2. 100(1- α) % Newcombe Score Confidence Interval for the Difference of Two Proportions ⁷

a. 100(1- α) % Wilson Score Confidence Interval for A Single Proportion⁵

$$\text{Lower Confidence Limit} = \left(\hat{p} + Z_{\alpha/2}^2 / 2n - Z_{\alpha/2} \sqrt{(\hat{p}(1 - \hat{p}) + Z_{\alpha/2}^2 / 4n) / n} \right) / \left(1 + Z_{\alpha/2}^2 / n \right)$$

$$\text{Upper Confidence Limit} = \left(\hat{p} + Z_{\alpha/2}^2 / 2n + Z_{\alpha/2} \sqrt{(\hat{p}(1 - \hat{p}) + Z_{\alpha/2}^2 / 4n) / n} \right) / \left(1 + Z_{\alpha/2}^2 / n \right)$$

where:

$$\hat{p} = x / n$$

n = sample size

x = number of "events"

$Z_{\alpha/2}$ = 100(1- $\alpha/2$)th percentile of the standard normal distribution

b. 100(1- α) % Newcombe Score Confidence Interval for the Difference of Two Proportions⁴

$$\text{Lower Confidence Limit} = (\hat{p}_1 - \hat{p}_2) - Z_{\alpha/2} \sqrt{L_1(1-L_1)/n_1 + U_2(1-U_2)/n_2}$$

$$\text{Upper Confidence Limit} = (\hat{p}_1 - \hat{p}_2) + Z_{\alpha/2} \sqrt{U_1(1-U_1)/n_1 + L_2(1-L_2)/n_2}$$

where:

\hat{p}_1 = sample proportion for group 1

\hat{p}_2 = sample proportion for group 2

L_1 and U_1 are the lower and upper Wilson Score confidence limits for p_1

L_2 and U_2 are the lower and upper Wilson Score confidence limits for p_2

$Z_{\alpha/2} = 100(1-\alpha/2)$ th percentile of the standard normal distribution

2.1.3 Propensity Score

Given that subjects in the two comparison groups (XIENCE 90 vs XIENCE V USA) are not randomized and thus may not have balanced baseline characteristics, the non-inferiority and superiority tests for 3-12 month period will be carried out through stratified analysis in the “3-month clear” population. The stratification will be performed through propensity scores (PS). For each individual a propensity score (i.e., predicted probability between 0 and 1) for group (XIENCE 90) membership will be calculated using logistics regression, with “group” as the outcome and baseline variables including demographic, lesion characteristics, and risk factors as the predictors. Subjects will be categorized into 5 groups based on the calculated propensity scores and their quintiles. Non-inferiority and superiority will then be carried out for the rate of the endpoint using the method described in sections below stratified by the propensity quintiles.

The propensity score modeling and design will be performed by an independent statistician who has no access to any outcome data of both the XIENCE 90 study and the XV USA historical control for the integrity and interpretability of study results. The independent statistician will be blinded and have no access to clinical outcome and any follow-up information to avoid introducing bias into the analysis.

[REDACTED]

[REDACTED]

[REDACTED]

[REDACTED]

[REDACTED]

Per the recent publication by Yue et al²⁸ on two-stage study designs involving propensity score adjustment, the propensity score calculation results will subsequently be sent to the FDA for review and approval prior to performing the primary endpoint and major secondary endpoint analyses.

[REDACTED]

2.1.3-1 Propensity Score Variable List

Based on prior clinical experience and clinical research, below is the list of variables that are considered to be related to assignments modeling building:

- Gender
- Age
- Creatinine
- Chronic anticoagulant
- History of stroke
- History of major bleeding
- Platelet
- Hb
- BMI
- Hypertension
- Dyslipidemia
- Prior PCI
- Prior CABG

- Prior MI
- Multivessel disease
- Clinical Presentation (ACS (NSTEMI, ACS unstable angina) vs. non-ACS)
- Diabetes
- ACC/AHA lesion complexity
- Total lesion length per patient
- RVD
- Diameter stenosis%
- Bifurcation
- Number of lesions treated
- Number of vessel treated
- Number of stents per patient
- Total stent length per patient
- Discharge P2Y12
- Paris bleeding score
- PRECISE DAPT score

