#### 6.1.2 *Clinical Assessments*

Subject demographics (age, gender, race), height, weight, family history of coronary artery disease (CAD), smoking status, cardiac history (myocardial infarction, diabetes mellitus, hypertension, hypercholesterolemia, and previous PCI/CABG information), subject's current cardiac status (presentation of CAD and multivessel disease) and indication of high bleeding risk (per criteria specified in Section 5.3.1.1) will be obtained and recorded in electronic case report form (eCRF).

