2.3 Subgroups for Analysis

All of the following subgroup analyses are intended for the primary analysis population. The comparison between the XIENCE 90 study and the XIENCE V USA historical control will be analyzed descriptively within each quintile for the primary and major secondary endpoints in a specific subgroup. The above quintiles are based on the overall PS, not PS built within each subgroup, as baseline characteristics of subjects are likely to be comparable in each quintile of the overall PS.

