2.3.4 Other Subgroups

The following subgroups will be evaluated for the primary analysis population for the primary and major secondary endpoints stratified by the overall PS. Analyses will be performed within the following subgroups:

- Ethnicity (white versus non-white)
- Age (age \geq median vs $<$ median)
- Age \geq 65 years old (US elderly patient)
- Clinical presentation (ACS NSTEMI, ACS unstable angina, non-ACS)

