2.7 Adjustments for Covariates

Unless otherwise specified, no adjustments for covariates will be made for any of the variables in the analyses.

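### The propensity score variable list omits race, although the SAP plans a white versus non-white comparison across both studies, so a possible difference in racial mix is not directly adjusted

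*SAP*

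**What the plan says.** - **Role of the score.** SAP 2.1.3 acknowledges that the two non-randomized groups might be unbalanced at baseline. It fits a logistic model for membership of XIENCE 90 and stratifies the non-inferiority and superiority tests by quintile of the fitted score. The predictors are described as demographics, lesion characteristics and risk factors.
- **The list.** SAP 2.1.3-1 opens with "Based on prior clinical experience and clinical research, below is the list of variables" and gives 29 items, from gender and age to two bleeding-risk scores. Neither race nor smoking appears.
- **What is collected.** Protocol 6.1.2 records "Subject demographics (age, gender, race), height, weight, family history of coronary artery disease (CAD), smoking status" and further history in the eCRF.
- **Subgroups.** SAP 2.3 states that "The comparison between the XIENCE 90 study and the XIENCE V USA historical control will be analyzed descriptively within each quintile". This applies to the primary endpoint and to both major secondary ones. The split in SAP 2.3.4 labelled ethnicity is white against non-white. SAP 2.3 uses quintiles of the overall score in every subgroup, on the ground that baseline characteristics are likely to be comparable within them.
- **Other adjustment.** SAP 2.7 says that "no adjustments for covariates will be made for any of the variables in the analyses", in a sentence that begins by excepting anything specified elsewhere.
- **Geography.** SAP 1.3 describes the control as a US post-approval study. XIENCE 90 has about 100 sites globally, with at least 50% of subjects in the US.

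**The concern.** The propensity score carries the confounding control in this comparison. It targets balance on the variables in its model, and balances others only as far as they correlate with those variables. Race is one of the three demographics that Protocol 6.1.2 names. The other two, age and gender, are on the list; race is absent and the visible text gives no reason. Missing control data cannot be that reason while the SAP plans a two-study comparison by race.

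A global cohort set against a US control makes a different racial mix plausible. If race is also associated with Death/MI or bleeding, given the listed variables, part of the difference between the studies would reflect who was enrolled and not how long DAPT was given. A shift in favour of XIENCE 90 would make a false non-inferiority or superiority claim more likely; a shift the other way would cost power.

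The race subgroup has a related weakness. The SAP's reason for reusing the overall quintiles is that they should make subjects comparable. For race, that comparability is not assured, because the model does not target it.

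**Working it through.** **1. The list against the data.** Of the 29 items in SAP 2.1.3-1, none is race, ethnicity or smoking. The variables compare as follows:

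| Variable | Collected in XIENCE 90 (Protocol 6.1.2) | Control data implied by the SAP | In the score |
|---|---|---|---|
| Age, gender | Yes | Yes | Yes |
| Race | Yes | Yes (2.3 with 2.3.4) | No |
| Smoking status | Yes | Not stated | No |

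**2. Other visible safeguards.** The geography test in SAP 2.6.1 compares US with non-US subjects inside XIENCE 90, so it cannot show a difference from the control. The visible sensitivity analyses replace quintiles with quartiles (2.2.1), remove subjects non-compliant with antiplatelet medication, or impute missing outcomes (2.9). None changes the covariates.

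**3. Possible size.** The documents give no prevalence of race in either study, no association with outcome, and no public margin or event rate. There is thus no figure in the plan to reproduce, and what follows is illustration on assumed inputs. For one binary factor left unadjusted:

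bias in the risk difference ≈ p0 × (RR − 1) × Δ

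where p0 is the risk without the factor, RR its relative risk and Δ the difference in its prevalence between the studies.

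The standard error uses the planned sizes in SAP 1.5 (2,000 and about 1,150):

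SE = √[p0(1 − p0)(1/2000 + 1/1150)]

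The chance of wrongly passing when the true difference equals the margin, if the shift favours XIENCE 90, is Φ(bias/SE − 1.96). Without bias this is the 0.025 of Protocol 9.4.

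| p0 | RR | Δ | Bias (points) | SE (points) | One-sided error |
|---|---|---|---|---|---|
| 5% | 1.3 | 5 points | 0.05 × 0.3 × 0.05 = 0.08 | 0.81 | 0.031 |
| 6% | 1.5 | 10 points | 0.06 × 0.5 × 0.10 = 0.30 | 0.88 | 0.053 |
| 6% | 2.0 | 15 points | 0.06 × 1.0 × 0.15 = 0.90 | 0.88 | 0.175 |

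Two simplifications matter. The formula allows no partial balance through correlated listed variables, which would shrink the bias. The 2,000 counts registered subjects, while the test uses only those who are 3-month clear, so the true standard error would be somewhat larger and the inflation somewhat smaller.

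**The case against.** The case for leaving the list alone has real parts.

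- **No imbalance is shown.** A reader might infer that a baseline difference in race is already known. The documents do not support this: they report no race or smoking distribution for either study, and the SAP says only that balance may be lacking.
- **Partial balance is likely.** A reader might infer that any race difference passes in full into the result, or that balance within the race subgroup is impossible. Neither follows. Stratifying on 29 variables will partly balance correlated factors, and the subgroup would be balanced if race were independent of study given those variables. The subgroup comparisons are also descriptive only.
- **The text is redacted and the design is reviewed.** SAP 2.7 carries an exception for anything specified elsewhere, and parts of 2.1.3 are blacked out. It cannot be said that every other adjustment is excluded or that balance checks are missing. An independent statistician without outcome access designs the score, and the FDA reviews it before the endpoint analyses. These are good safeguards, but they do not put race on the visible list.
- **Smoking is a weaker case.** It is documented only in XIENCE 90. It might also enter through "Paris bleeding score" or "PRECISE DAPT score", whose components the SAP does not give. It is not a planned subgroup, so the argument from SAP 2.3.4 does not reach it.
- **LVEF.** A reader might extend the point to LVEF because it is used to select both groups. It serves there as a threshold, and Protocol 6.1.2 does not list it among the baseline data. The extension is not supported.
- **Adjustment has limits.** If race predicts study membership but not outcome, adding it costs some overlap and precision without reducing bias. Nor can it supply non-US controls. Both points stand; the first is a small cost.

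**Conclusion.** The point holds for race. The plan records it, presumes it is available for the control, plans to compare the studies within it, and leaves it out of the score without a visible reason. What can be said is that a possible difference is not directly adjusted, and that comparability in the race subgroup is not assured.

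The size is unknown. The illustrative shift of about 0.08 to 0.9 percentage points rests wholly on the assumed base rate, relative risk and prevalence difference. It runs from negligible to about one standard error, and could go in either direction. The margin is not public, so the shift cannot be scaled against it. The reason to act is that the adjustment is simple and can be made before outcomes are seen. For smoking, the point is conditional on the control data.

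**What to change.** 1. Add race (white/non-white) to SAP list 2.1.3-1 at the outcome-blinded design stage, before the score goes to the FDA. Handle missing values with the multiple imputation already planned in SAP 2.5.
2. Ask the independent statistician whether XIENCE V USA recorded smoking status. Add it only if so.
3. Report standardized differences for these variables, before and after stratification, with the score results.

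Cost: the list grows from 29 variables to 30, or to 31 with smoking. Race needs no new collection in XIENCE 90, and the planned subgroup already presumes it in the control. There may be a small loss of overlap or precision if race predicts study membership but not outcome. The lack of non-US controls remains and should be stated as a limitation.

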2.1.4 Hypothesis Testing

Primary endpoint analysis for 3-month DAPT

The XIENCE 90 study is powered based on primary endpoint of Death/MI between 3-month and 12-month follow-up. Death/MI is defined as the composite endpoint of all death or all myocardial infarction (Academic Research Consortium [ARC]). This primary endpoint will be evaluated between XIENCE 90 and XIENCE V USA historical control stratified by propensity score quintiles in the primary analysis population.

The stratified Farrington-Manning method will be performed to test non-inferiority (NI) of 3-month DAPT from XIENCE 90 compared to standard DAPT duration up to 12 months from

XIENCE V USA historical control. [REDACTED]

[REDACTED]

[REDACTED]

[REDACTED]

[REDACTED]

[REDACTED]

[REDACTED]

$$\hat{\delta}_i = p_{it} - p_{ic}$$

$$w_i = \frac{(N_{it} + N_{ic})}{\sum_i (N_{it} + N_{ic})}$$

$$V(\hat{\delta}_i) = \frac{p_{imt}(1-p_{imt})}{N_{it}} + \frac{p_{imc}(1-p_{imc})}{N_{ic}}$$

P_{imt} and P_{imc} are calculated as follows:

$$r_i = N_{it}/N_{ic}$$

$$a1 = - (1 + r_i + p_{ic} + r_i * p_{it} - \delta * (r_i + 2))$$

$$a2 = \delta ** 2 - \delta * (2 * p_{ic} + r_i + 1) + p_{ic} + r_i * p_{it}$$

$$a3 = p_{ic} * \delta * (1 - \delta)$$

$$u = a1**3 / (3 + 3 * r_i) ** 3 - a1 * a2 / (6 * (1 + r_i) ** 2) + a3 / (2 + 2 * r_i)$$

$$v = \text{sign}(u) * \sqrt{a1**2 / ((3 + 3 * r_i) ** 2) - a2 / (3 + 3 * r_i) }$$

$$w = 1 / 3 * (\text{arcos}(-1) + \text{arcos}(u / v ** 3))$$

$$p_{imc} = 2 * v * \cos(w) - a1 / (3 + 3 * r_i)$$

$$p_{imt} = p_{imc} + \delta$$

Major secondary endpoints analyses for 3-month DAPT

If the hypothesis testing for the primary endpoint is successful, the hypotheses testing for the major secondary endpoint #1 will be performed followed by the hypotheses test for the major secondary endpoint #2.

I. Major Secondary Endpoint #1: Bleeding rate (BARC type 2-5) from 3- to 12-month follow-up

The superiority test for the major secondary endpoint #1 will be performed stratified by propensity score quintiles in the primary analysis population.

[REDACTED]

[REDACTED]

[REDACTED]

[REDACTED]

[REDACTED]

II. Major Secondary Endpoint #2: Stent Thrombosis (ARC definite/probable) from 3- to 12-month follow-up

The exact test will be performed for major secondary endpoint #2 in the primary analysis population.

[REDACTED]

This test will be performed if the superiority of major secondary endpoint #1 is established.

2.1.5 Survival Analyses

Survival analysis may be conducted to analyze time-to-event variables. Subjects without events will be censored at their last known event-free time point. Survival curves will be constructed using Kaplan-Meier estimates.

Summary tables for the endpoints will include failure rates (Kaplan-Meier estimates). For the primary analysis report, all available data will be used.

2.2 Endpoint Analyses

2.2.1 Primary Endpoint Analysis

Primary Analysis:

A non-inferiority test will be performed on the primary endpoint for the primary analysis population of the XIENCE 90 study and the XIENCE V USA historical control stratified by propensity score quintiles [REDACTED].

To ensure all subjects to be included in this analysis, multiple imputations will be performed in calculating the propensity scores.

Secondary Analysis (as a sensitivity analysis):

In addition to the primary analysis stratified by propensity score quintile, a non-inferiority test will be performed on the primary endpoint stratified by propensity score quartile, with the same methodology as described above.

